Safety and tolerability will be assessed by collating data on treatment-emergent adverse 428 429 events (AE), laboratory tests, physical examinations, and vital signs. Prevention of pregnancy will be monitored monthly by both laboratory and home pregnancy testing. All patients will be 430 431 educated about not becoming pregnant and perform monthly urine home pregnancy tests during the months that they do not have laboratory evaluations. Patients will be educated 432 about the side effects and use of liraglutide 3.0 mg and the injection delivery system. Liraglutide 433 434 3.0 mg is a well-tolerated long-term weight loss agent. The most common expected AEs (prevalence >5%) are nausea, diarrhea, constipation, vomiting, dyspepsia, fatigue, dizziness, and 435 abdominal pain (see reference 77 - prescribing information). Patients will be asked about the 436 most common adverse events related to liraglutide such as nausea, headache, diarrhea, 437 constipation and vomiting if not volunteered. This protocol and the associated Informed 438 439 Consent as well as any addenda or amendments, must be reviewed and approved by the Woman's Hospital Institutional Review Board (WHIRB) review committee prior to the start of the 440 study. All revisions to this Protocol are considered "protocol amendments; these must be 441 approved in advance, in writing, by the WHIRB. Every patient will have given her written 442 443 informed consent prior to participating in the study. Prior to participation in this trial, each subject will have an opportunity to ask questions and will sign (and date) a written Informed 444 Consent, which must be witnessed. The signed consent forms will be filed with the 445

investigator's study charts for each subject. Any subject may voluntarily withdraw from thestudy at any time without prejudicing treatment.

448

449 STUDY PLANS AND PROCEDURES

450 Subjects

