During the study period, cycle control will be assessed daily by the subjects using a menstrual diary. Vaginal bleeding will be classified by the subject as either spotting (requiring at least one pad/tampon per day) or bleeding (two or more pads/ tampons per day). The effects of treatment intervention on menstrual abnormalities will be evaluated by assessing posttreatment changes in menstruation frequency over 30 weeks from the patient's menstrual cycle diary and normalized to the number of menstruations per year (52 weeks).

All side-effects will also be recorded and summarized for the 30 week-treatment period. During the whole study period, compliance to the treatment will be documented. Compliance with treatment will be checked by questioning about the side-effects and a subjective evaluation of the tolerability of the administered drug; the patients will also asked about incidental missed administrations and whether they had correctly followed the scheduled treatment. Questioning regarding the occurrence of adverse events and use of concomitant medication will take place throughout the trial.

655

656 Study Medication

657 Study Drug Storage- All investigational products (study drugs) will be stored under 658 appropriate storage conditions in a secure area according to local regulations. The investigator is responsible for ensuring that it is dispensed only to study subjects and only from official study 659 660 sites by authorized personnel, as dictated by local regulations. The investigator is responsible for 661 ensuring that the investigational product is stored under the appropriate environmental 662 conditions (temperature, light, and humidity), as noted in the product labeling. Novo Nordisk 663 will supply all investigational products. The distribution of all supplied medications is the 664 investigators' responsibility.

665 *Study Drug Records*- It is the responsibility of the investigator to ensure that the 666 unblinded study coordinator maintains a current disposition record of investigational product. 667 Records or logs must comply with applicable regulations and guidelines and should include:

- 668
- 669

672 673

674

675

- amount received and placed in storage area; amount currently in storage area
- label ID number or batch number
- amount dispensed to and returned by each subject, including unique subject
 identifiers
 - non-study disposition (e.g., lost, wasted)
 - amount destroyed at study site

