The United States Food and Drug Administration (FDA) have assigned pregnancy category X to Saxenda (3 mg liraglutide). Studies in animals or humans have demonstrated there is positive evidence of human fetal risk based on adverse reaction data from investigational or marketing experience, and the risks involved in use of the drug in pregnant women clearly outweigh potential benefits. Safer alternatives exist. If patients become pregnant during the study, all medications will be stopped and the patient will discontinue from the study.

For safety, all subjects who enter the study are evaluable. Subjects will be monitored for safety by assessment of adverse events, physical exams, vital signs and laboratory values. Continued patient safety assessment will be carried out and all adverse events documented and reported to the WHIRB. On each visit, compliance with treatment will be checked with questions about the side-effects and a subjective evaluation of the tolerability of the administered drug; the patients will also asked about incidental missed administrations.

Adverse events will be evaluated on a continuous basis while the patient is on study and until 30 days after the last dose of study drug. Patients should be followed until all treatmentrelated adverse events have recovered to baseline or are deemed irreversible by the principal investigator.

826

827 Adverse Event Procedures

An Adverse Event (AE) is defined as any new untoward medical occurrence or worsening of a preexisting medical condition in a clinical investigation subject administered an investigational (medicinal) product and that does not necessarily have a causal relationship with this treatment. An AE can therefore be any unfavorable and unintended sign (such as an abnormal laboratory finding), symptom, or disease temporally associated with the use of investigational product, whether or not considered related to the investigational product.

An Adverse Reaction (AR) is defined as any untoward and unintended responses to an investigational medicinal product related to any dose administered Thus, for an AR, a causal relationship must be at least suspected by the medical practitioner. Unexpected Adverse Reaction (UAR) is an adverse reaction, the nature or severity of which is not consistent with the applicable product information (e.g. investigator's brochure for an investigational product or summary of product characteristics for an authorized product).

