- The causal relationship to study drug is determined by a physician and should be used to
- assess all adverse events (AE). The casual relationship can be one of the following:
 Related: There is a reasonable causal relationship between study drug administration and
 the AE.
- 844 Not related: There is not a reasonable causal relationship between study drug 845 administration and the AE.
- The term "reasonable causal relationship" means there is evidence to suggest a causal relationship.
- Adverse events can be spontaneously reported or elicited during open-ended questioning, examination, or evaluation of a subject. (In order to prevent reporting bias, subjects should not be questioned regarding the specific occurrence of one or more AEs.)

Serious Adverse Event (SAE) or Serious Adverse Reaction (SAR) or Suspected Unexpected Serious Adverse Reaction (SUSAR)

- A serious adverse event (experience) or adverse reaction is any untoward medical
- 854 occurrence that at any dose:
- 855 results in death
- is life-threatening (defined as an event in which the subject was at risk of death at the time
 of the event; it does not refer to an event which hypothetically might have caused death if it
 were more severe)
- requires inpatient hospitalization or causes prolongation of existing hospitalization (see
 NOTE below)
- results in persistent or significant disability/incapacity
- is a congenital anomaly/birth defect
- is an important medical event (defined as a medical event(s) that may not be immediately 863 life-threatening or result in death or hospitalization but, based upon appropriate medical 864 and scientific judgment, may jeopardize the subject or may require intervention [e.g., 865 medical, surgical] to prevent one of the other serious outcomes listed in the definition 866 above.) Examples of such events include, but are not limited to, intensive treatment in an 867 emergency room or at home for allergic bronchospasm; blood dyscrasias or convulsions that 868 869 do not result in hospitalization.) Potential drug induced liver injury (DILI) is also considered 870 an important medical event.
- 871 Serious adverse reaction (SAR): an adverse event fulfilling both the criteria for a Serious Adverse 872 event (SAE) and the criteria for an Adverse Reaction (ADR).
- A Suspected Unexpected Serious Adverse Reaction is known as a SUSAR. Sometimes during a clinical trial, there may be serious adverse reactions in subjects given the drug, which may or

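### The protocol tells staff both to ask about named common side effects and not to ask about specific adverse events, so rates of those symptoms would rest on an unrecorded mix of methods

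*Combined protocol and SAP*

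**What the plan says.** Two sections of the combined protocol and SAP say how symptoms are to be elicited.

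- **Safety variables/Measures** states that patients will be asked about the "most common adverse events related to liraglutide such as nausea, headache, diarrhea", and the sentence continues "constipation and vomiting if not volunteered". This is a direct prompt, used when the woman has not raised the symptom.
- **Adverse Event Procedures** sets out the permitted routes: "Adverse events can be spontaneously reported or elicited during open-ended questioning, examination, or evaluation of a subject". It then adds in parentheses, as a guard against biased reporting, that "subjects should not be questioned regarding the specific occurrence of one or more AEs".

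Two further places mention questioning without saying whether it is prompted or open.

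- **Study Assessments** says "Compliance with treatment will be checked by questioning about the side-effects", and later "Questioning regarding the occurrence of adverse events and use of concomitant medication will take place throughout the trial".
- **Ethical and Regulatory Requirements** says that at each visit "compliance with treatment will be checked with questions about the side-effects and a subjective evaluation of the tolerability of the administered drug".

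The Safety assessments section puts the frequency and severity of adverse events first among its safety and tolerability measures. The Statistical Methods section plans no test of adverse events between arms. Study Assessments says only that side effects will be recorded and summarized over the treatment period.

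**The concern.** The two instructions are both current text and cover the same women over the same period. If a woman has nausea and does not mention it, one section tells staff to ask her about it and the other tells them not to. Because the protocol also requires conduct in compliance with its own text, staff depart from one instruction whichever they choose.

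The symptoms affected are mainly the gastrointestinal effects that the Benefit/Risk section calls the most common with this drug class, so they will probably carry most of the tolerability description. Prompted and unprompted questioning generally give different counts. If some staff prompt and others do not, or the same person does so at a clinic visit but not on a monthly call, the reported percentage reflects a blend of methods that the record does not show. A reader could not say what a reported nausea rate measures, or set it beside a rate from another trial with a known method. Once the data are collected without a marker, the two kinds of report cannot reliably be separated.

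**Working it through.** The plan gives no figure to reproduce, so the main check is a comparison of the text.

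| Question | Safety variables/Measures | Adverse Event Procedures |
|---|---|---|
| May staff ask about a named symptom? | Yes, patients will be asked | No, subjects should not be asked |
| When does the rule apply? | When the woman has not volunteered the symptom | No exception is stated |
| Which symptoms? | Five are named, introduced as examples | Any specific adverse event |
| Reason given | None | Reporting bias |

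1. *Can both be followed?* If the symptom is volunteered, yes, because no prompt is needed. If it is not volunteered, no.
2. *Does another section settle it?* No. Study Assessments and Ethical and Regulatory Requirements call for questions about side effects but leave their form open. No text ranks the rules, exempts the named symptoms, or separates solicited from unsolicited events.
3. *Is the prompt list fixed?* No. Its five symptoms are only examples. It includes headache, which is absent from the same section's list of events expected in more than 5% of patients. It omits dyspepsia, fatigue, dizziness and abdominal pain, which are on that list. Two people who both prompt could therefore prompt for different things.
4. *Can the effect be sized?* Let p be the true proportion with a symptom, c the share of true cases that a method picks up, and f the share of women without the symptom who report it anyway. If c and f are equal in both arms:
   - observed rate = c × p + f × (1 − p)
   - observed risk difference = (c − f) × (p in the liraglutide arm − p in the placebo arm)
   - with mixed methods, c and f are averages weighted by the share of questioning that was prompted.

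The documents give none of p, c, f or that share, so the size cannot be calculated. The values below are assumptions chosen only to show how the quantities behave: true nausea of 40% against 15%, with capture from 50% to 100%. The last row uses f = 0.25, the value that makes c − f equal 0.75 when c = 1.

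| c | f | Liraglutide | Placebo | Difference (points) | Ratio |
|---|---|---|---|---|---|
| 1.00 | 0 | 40% | 15% | 25 | 40/15 = 2.67 |
| 0.75 | 0 | 30% | 11.25% | 18.75 | 30/11.25 = 2.67 |
| 0.50 | 0 | 20% | 7.5% | 12.5 | 20/7.5 = 2.67 |
| 1.00 | 0.25 | 0.40 + 0.25 × 0.60 = 55% | 0.15 + 0.25 × 0.85 = 36.25% | 18.75 | 55/36.25 = 1.52 |

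Rows 2 and 4 have the same risk difference, but their liraglutide rates are 55 − 30 = 25 points apart. Missed symptoms and suggested symptoms can each dilute the difference, so the algebra does not show which method is better. It shows that rates and differences depend on the method, and that an unrecorded mix leaves a reader unable to tell which row applies.

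**The case against.** The strongest case on the other side has four parts.

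- *The specific rule may be meant to override the general one.* The prompting sentence is about this drug, the restriction sits in general adverse-event text, and its wording is advisory. That is a reasonable guess at intent. But the document does not say so, and the reason given for the restriction, reporting bias, applies directly to prompting for a drug's known effects.
- *Blinding protects the comparison.* Investigators and participants do not know the allocation, so inconsistent questioning should be unrelated to arm. This stands. A reader might infer that the adverse-event rates become uninterpretable or that the arms can no longer be compared. The documents do not support that: the comparison may be diluted or noisier, but it is not invalid. With equal capture and no suggested reports, the risk ratio does not change at all.
- *The scope is narrow.* Serious events, laboratory abnormalities, vital signs, examinations and withdrawals for adverse events do not depend on prompting to any great extent. No efficacy endpoint and no planned test rests on symptom rates. This also stands.
- *Any figure is invented.* A reader might take the first three rows of the illustration as the loss to expect. They are not an estimate: every input is assumed, they describe uniform under-capture and not a mix of methods, and they leave out suggested reports. The last row is there to show that prompting can shrink the difference too.

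Nor do the documents show that prompting should win. Removing the prompting sentence would end the contradiction equally well.

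**Conclusion.** The point holds as an internal contradiction that should be corrected. For a common symptom that a woman does not volunteer, staff cannot comply with both sections, and the protocol gives no way to choose between them. The consequence is limited to the absolute rates and risk differences of these symptoms, which would depend on a mix of elicitation methods that is not recorded. Its size cannot be derived from the documents.

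Two assumptions support the conclusion that the arm comparison survives: the people asking the questions are among those blinded, and whatever mix of methods arises is the same in both arms. The protocol provides for an unblinded research assistant and an unblinded study coordinator, but the tasks it gives them concern randomization and drug supply, not adverse-event questioning.

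**What to change.** Reconcile Safety variables/Measures and Adverse Event Procedures to one elicitation procedure, used identically for every woman at every visit and call, and align the side-effect questions in Study Assessments and Ethical and Regulatory Requirements with it. Two options would do this.

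1. *Open question, then checklist.* Ask an open-ended question first, then go through a closed list of the named symptoms in fixed wording. Record each event as volunteered or solicited, and tabulate the two separately by arm. This keeps the systematic capture that one section wants and lets a reader see the reporting bias that the other section fears.
2. *No prompting.* Delete the prompting sentence and rely on the routes listed under Adverse Event Procedures.

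The first option costs some protocol wording, a short checklist and one extra field on the adverse-event page. Its downside is that prompted rates may be higher and may include some suggested reports, although the marker makes these visible. The second costs only wording; its downside is that some unvolunteered symptoms may be missed. Neither changes any dose, schedule or treatment rule.
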